Discontinuation of study medications will be managed without unblinding. Participants will be encouraged to remain in the study and complete measurements per protocol to be included in the intention-to-treat analysis. One exception to this is if a participant develops a "serious" Adverse Event in which case he/she will not be asked to remain in the study. If there is an Adverse Event which is thought by the staff to be "probably related" or "related" to the coded medication, the PI, when necessary for the safety of the participant, will contact [name] the unblinded team member, and ask him to provide the treatment assignment to the participant's physician. A detailed written report will be submitted to the IRB.

To optimize intra-study safety and tolerability, we will take the following steps:

- upon enrollment, give each participant a wallet card containing name, dates in study, study treatments (whey protein or isocaloric placebo powder per day; 81 mmol KHCO₃ or matching placebo per day) and contact information where the study physician ([name], PI) can be reached during the day and evening/weekend hours;
- instruct participants to notify [name] *before* starting *any* new drugs during this study (because some medications impair potassium excretion and increase risk of hyperkalemia);
- instruct participants to notify [name] of any changes in health status or of any hospitalizations or emergency room visits;

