- monitor serum potassium (K) at baseline, 6 wks on full 81 mmol/d dose and at the end of study at 24 wks. In addition, we will measure serum K at 1 week if the participant is on an ACEI, ARB or potassium sparing diuretic. We will measure serum K at any other time, should a participant experience an AE which might be related to the trial. In the unlikely event that it is elevated, the measurement will be repeated immediately. If the repeat measure is elevated, all study pills will be stopped. Serum K will be re-measured after one day off of the study pills to ensure that it has returned to normal. If it remains elevated, the participant will be referred immediately to his/her doctor. Discontinuation of study medications will be managed without unblinding. Participants will be encouraged to remain in the study and complete measurements per protocol to be included in the intention to treat analysis. One exception to this is if a participant develops a "serious" AE in which case he/she will not be asked to remain in the study. If there is an AE which is thought by the staff to be "probably related" or "related" to the coded medication, the PI, when necessary for the safety of the participant, will contact [name], the unblinded team member, and ask her to provide the treatment assignment to the participant's physician. A detailed written report will be submitted to the IRB.

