- monitor GFR after 6 wks in the study and at the final 24-wk visit. GFR will be monitored because the higher protein intake and progressive renal failure increases risk of hyperkalemia. The study inclusion criteria include a GFR \geq 50 ml/min/1.73m². If GFR falls below 45 ml/min/1.73 m², participants will be asked to return for a repeat measurement the following day. Should the participant be unable or unwilling to return for the repeat study blood, study interventions (powder packets and pills) will be discontinued. Participants who fail to show up for repeat monitoring will be contacted and advised to obtain care as soon as possible. If the repeat measure is normal, the participant continues per protocol. If the repeat GFR is below 45 ml/min/1.73 m², the study powder and pills will be stopped and the participant referred to his/her physician for follow-up care. If the repeat GFR is in the range of 45-50 ml/min/1.73m², the participant will remain on study capsules and be asked to return for a follow-up GFR measurement in the next week. If the GFR is again less than 45 ml/min/1.73, the participant will stop study capsules and be referred to his care giver for follow-up. If it is above 45 ml/min/1.73, the participant will continue taking study pills. Participants discontinuing study capsules will remain in the study for the intent-to-treat analysis. The threshold of 45 ml/min/1.73 m² was chosen to allow for some day to day fluctuation in creatinine and hydration status. Any decline below 45 ml/min/1.73 m² will be recorded as an Adverse Event.
- have all pill supplements taken in split doses after meals with a full (8-oz) glass of water to increase tolerability;
- have all powder packet supplements incorporated in each meal in split doses to increase tolerability;
- phase-in treatment for study pills (taking half dose for the first 14 days) to increase tolerability

- have participants who are unable to tolerate an escalation of the study pills or packets remain in the study and take the maximal number of capsules or powder packets that they are able to tolerate.

Data Safety and Monitoring Board (DSMB)

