To help ensure safety of participants and the validity and integrity of the data, a DSMB was established to monitor this trial. This was done in accordance with NIH policy. This board have reviewed and approved the plans and safety and overall operations and have approved the Manual of Operating Procedures before the trial begins. The members of the DSMB were chosen by the NIA to have the relevant scientific and medical knowledge to monitor this trial. This board includes two experts in the field of dietary protein and acid-base and a statistician. Names of candidates have been provided by the NIA. In addition, the Program Officer, [name] PhD, from the NIA who is responsible for this trial is included. DSMB members have no conflicts of interest related to the trial. Administrative and safety summaries will be sent to the DSMB at the requested intervals during the trial. These reports will describe the numbers of participants screened, enrolled, and completed, and summaries of the baseline characteristics of the enrollees and of adverse events.

Adverse event (AE) reporting

- All AEs (“expected or “unexpected”) and/or laboratory abnormalities and/or problems will be recorded on AE forms and include a brief narrative description including onset, duration, whether the AE has resolved, whether it was expected or unexpected, and whether any treatment was administered for the AE.
- Severity of AEs will be described (“serious” or “non-serious”). Serious AEs, whether or not related to the trial, will be reported to IRB and DSMB immediately (within 24 hours) by phone and in writing. Other AEs will be reported within 5 days to the IRB and at the requested interval to the DSMB.

Other IRB reports

- All serious AEs and any AE that results in the participant’s withdrawal from the study or deviation from the study protocol.
- New information that may adversely affect safety of participants or conduct of trial.
- If applicable, recent literature relevant to the hypothesis related to the trial to determine whether continuation of the trial is ethical in the setting of new information.
- All proposed protocol modifications or additions.
- Annual continuing review, listing study progress and all AEs.

Unanticipated problem and adverse event (AE) reporting

This will be done in accordance with the Tufts IRB Reportable New Information policy.

Confidentiality

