For all objectives, we use a superiority framework and a factorial analysis (at-the-margins analysis), i.e., testing the superiority of whey protein against no whey protein and of KHCO₃ against no KHCO₃.

e. Statistical interim analyses and stopping guidance

No formal statistical interim analysis was planned. The Data and Safety Monitoring Board (DSMB) periodically evaluated enrollment data, AE, and SAE by randomization group.

f. Timing of final analysis

Final analysis will take place after all data for the primary and secondary outcomes have been collected, data cleaning is complete, and after this SAP is finalized and posted on clinicaltrials.gov.

g. Timing of outcome assessments

Outcomes are measured at baseline, 12 weeks, and 24 weeks after randomization.

5. Statistical Principles

a. Confidence intervals and P values

All statistical tests will be 2-sided. We will use $p \leq 0.05$ to indicate statistical significance for the primary outcome for each of the two primary comparisons of interest in a factorial analysis (at-the-margins analysis): a) the comparison between all participants allocated to KHCO₃ vs. all those not allocated to KHCO₃ and b) the comparison between all participants allocated to whey protein vs. all those not allocated to whey protein. Under the assumption of no interaction that is inherent to a factorial analysis, the primary analyses test two independent hypotheses, and no multiplicity adjustment is needed in this scenario. All secondary and exploratory analyses are considered as supporting the primary analyses, with two-sided tests and significance levels of 0.05.

b. Adherence and protocol deviations

Adherence to study pills was assessed by capsule counts and by capsule diaries. Adherence to the protein packets was assessed by packet counts and diaries. Objective measures of adherence are urinary net acid excretion (NAE) and UNi.

Major protocol deviations for the trial include:

1. Participant found ineligible after randomization
2. No informed consent signed
3. Participant didn't receive the randomly allocated intervention
4. Withdrawal of consent for future data collection, and/or ongoing use of previously collected study data

c. Analysis populations

The full analysis set will include all randomized subjects. Following the intention-to-treat (ITT) principle, subjects will be analyzed according to the group they were assigned to at randomization regardless of treatments received.

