- Health ABC-PPB score at 24 weeks
- 24hr urinary nitrogen excretion

Exploratory:

- muscle mass as measured by D₃-creatine dilution at 24 weeks

b. Analysis methods

Summary statistics. For each outcome, we first will report summary statistics at each timepoint for whey protein vs. no whey protein and for KHCO₃ vs. no KHCO₃. We will then report summary statistics in each of the four cells of the 2x2 design. We also will create box plots that display the distribution of the data at each time point for each comparison.

Primary Outcome. Primary analyses of the primary outcome will be performed on the ITT sample based on an ANCOVA comparing 24-week leg power with fixed effects for intervention groups and further adjustment for leg power at baseline, age and sex. Moreover, the effect of each intervention will be adjusted for the other intervention. Type III sum-of-squares will be used to test significance of each intervention. Least squares mean difference between intervention groups, and 95% confidence intervals, based on the fitted linear models will be reported.

Table 2: Presentation of the results of the primary analyses

	Whey protein	No whey protein	KHCO ₃	no KHCO ₃
Leg power, mean (SD)	xx.x (xx.x)	xx.x (xx.x)	xx.x (xx.x)	xx.x (xx.x)
LS mean difference (95% CI)*		-xx.xx (-xx.x to -xx.x)		-xx.xx (-xx.x to -xx.x)
p value		xxx		Xxx

*adjusted for sex, age, leg power at baseline, and factorial design

Secondary analyses and secondary outcomes.

- We also will conduct factorial analyses of all secondary outcomes by using similar analytic approach to the primary outcome.
- In addition of ANCOVA analyses, we will fit longitudinal model based on all repeated measurements of the outcome, i.e., a linear model with 12-week and 24-week measurements as outcome observations and fixed effects for the intervention group, time treated as categorical, intervention group by time interaction, baseline measure, baseline measure by time interaction, and sex. The corresponding treatment effect measure is the between-group difference in the slopes of the mean responses. Restricted maximum likelihood estimation will be used with the Newton–Raphson algorithm. An unstructured covariance matrix will be used to model the variance-covariance matrix for random intercept and random slope. In the case of nonconvergence with UN, a toeplitz covariance matrix will be used. In the case of nonconvergence with TOEP, an autoregressive covariance matrix [AR (1)] will be used.

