Difference in estimated least square mean slopes, the corresponding 95% CI, and p-value will be reported. We will use the p value from the type III F-test of the fixed effect parameter for the intervention group by time interaction. Denominator degrees of freedom will be estimated using the Kenward-Roger approximation with an unstructured covariance matrix and the between-within method otherwise.

- We also will present results for outcome measures at follow-up within each of the four factorial groups in the 2×2 design. We will test for interaction by extending the multivariable linear models described above by simply adding the appropriate interaction terms. However, we anticipate insufficient precision on the interaction estimates to rule out interaction.
- We will repeat analyses in the mITT and per protocol samples.

c. Subgroup Analyses

We will perform subgroup analyses by sex, NAE (<15 mmol/day vs. ≥ 15 mmol/day), protein intake based on average 3-day food recall (≤ 0.8 gm/kg/day vs. > 0.8 gm/kg/day), no sarcopenia vs. sarcopenia (defined as maximum grip strength <35.5 kg (men) and <20 kg (women) in either hand and/or gait speed <0.8 m/sec.

d. Missing data

Descriptive tables of baseline characteristics stratified by arm will include the frequency and percentage of missing values. In attrition analyses, we will then compare these variables between subjects who drop out and subjects with complete outcome data. The number of missing primary outcome data points at each time point, by intervention arm, will be reported in the CONSORT participant flow diagram.

For the primary analyses, we will analyze all available follow-up outcome data using restricted maximum likelihood estimation, under the assumption that data are missing at random.

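### Outcome measurement is not sought after a serious adverse event, and neither the primary analysis nor the planned imputation accounts for the resulting missing leg-power data

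*Protocol*

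**What the plan says.** **Protocol, Protection of study blinding.** The general rule for those who stop study product is: "Participants will be encouraged to remain in the study and complete measurements per protocol to be included in the intention-to-treat analysis". The exception follows at once: a participant who develops a serious "Adverse Event in which case he/she will not be asked to remain in the study". The potassium-monitoring item in the list of safety steps under the same heading repeats it: "AE in which case he/she will not be asked to remain in the study".

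**Protocol, other reasons for stopping.** The GFR-monitoring item takes the opposite line: "Participants discontinuing study capsules will remain in the study for the intent-to-treat analysis". Protections Against Risk likewise keeps in the study those who cannot tolerate the full amount of pills or powder.

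**Protocol, Adverse event (AE) reporting.** Expedited reporting applies to "Serious AEs, whether or not related to the trial". The exception itself does not mention relatedness.

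**SAP 5c.** "The full analysis set will include all randomized subjects", analysed as assigned.

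**SAP 7b.** The primary analysis is an "ANCOVA comparing 24-week leg power with fixed effects for intervention groups and further adjustment for leg power at baseline, age and sex", with each factor also adjusted for the other.

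**SAP 7d.** Available follow-up data are analysed by restricted maximum likelihood "under the assumption that data are missing at random". The sensitivity analysis is multiple imputation by chained equations. Candidate auxiliaries are randomisation group, stratification factors, baseline variables and outcome data. Other strategies are left open and none is named.

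**The concern.** The general rule does what an ITT analysis needs: stopping the product does not stop the measurements. The exception withdraws that request from one group, and membership of the group is decided by a health event after randomisation. A hospitalisation or similar event may well reduce leg power, so the missing values could be systematically lower than the model would predict from baseline power, age and sex. Missing at random would then fail for these participants.

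If such losses differ between whey and no whey, or between KHCO₃ and no KHCO₃, the corresponding marginal comparison is biased for the ITT effect. Nothing named in the SAP would show by how much.

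**Working it through.** **1. The plan's own figures (SAP 4c), for scale.** Power = Φ(difference / (SD × √(2/60)) − 1.96), with 60 per level and two-sided 0.05.

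- KHCO₃: SE = 12 × √(2/60) = 2.19; 6/2.19 = 2.74; power = 78.2% (77.5% with the t distribution), against a stated 80%.
- Whey: SE = 15 × √(2/60) = 2.74; 8/2.74 = 2.92; power = 83.2% (82.6% with t), against a stated 80%.

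These fix the scale: planned effects of 6 and 8 percentage points of change in power. The present point does not depend on them.

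**2. What each analysis does with a participant who has no 24-week value after an SAE.**

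- *Primary ANCOVA (7b).* There is one outcome row per person. A participant without that row contributes nothing, and restricted maximum likelihood cannot recover it. This is in effect a complete-case analysis.
- *Longitudinal model (7b, secondary).* It uses a week-12 value if there is one. A value taken before the event carries no information on what the event did, and the model still relies on missing at random.
- *Multiple imputation (7d).* It also relies on missing at random. SAE status is not among the listed auxiliaries, so these participants would be imputed as if they resembled event-free participants with the same history.
- *Missing-not-at-random analysis.* None is named.

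**3. Size of the possible bias.** Let f₁ and f₀ be the shares of the active and control levels that go unmeasured because of an SAE. Let D₁ and D₀ be how far their true mean falls below the model's prediction. Each level's mean is then overstated by its own f × D, so

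bias (estimated minus true ITT difference) = f₁D₁ − f₀D₀, which is D × (f₁ − f₀) when the shortfall is the same in both levels.

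The documents give neither an SAE rate nor a shortfall, so every input below is an assumption. D runs from 6 to 24 points, which is 0.5 to 2 SD at the KHCO₃ SD of 12.

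| Loss, active vs control | D = 6 | D = 12 | D = 24 |
|---|---|---|---|
| 2% vs 2%, or 5% vs 5% | 0 | 0 | 0 |
| 5% vs 2% | 0.18 | 0.36 | 0.72 |
| 10% vs 5% | 0.30 | 0.60 | 1.20 |
| 10% vs 0% | 0.60 | 1.20 | 2.40 |

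The non-zero range of 0.18 to 2.4 points is 3% to 40% of the 6-point KHCO₃ effect and about 2% to 30% of the 8-point whey effect. A loss difference of 3 to 10 percentage points is about 2 to 6 people in a level of 60 (0.03 × 60 = 1.8; 0.10 × 60 = 6). If the greater loss is in the control level, the sign reverses and the effect is understated.

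The scale is percentage change, as in SAP 4c. The primary ANCOVA analyses the 24-week value itself, so the table shows proportions of the planned effect rather than a forecast.

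**4. Precision.** If 1 to 6 of 60 per level are unmeasured and not replaced, power (normal approximation) is 77.5% to 73.8% for KHCO₃ and 82.6% to 79.1% for whey. The protocol targets 120 completers, so further recruitment may make up the number. It would not remove a bias.

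**The case against.** **The ITT set is not contradicted.** A reader might infer that the exception conflicts with a set of all randomised subjects. It does not. SAP 5c says who is counted and how they are classified, not that every outcome will be observed. The exception undercuts the set by leaving outcomes unsought. This objection stands.

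**Nobody is removed.** A reader might also infer that the sickest participants are taken out. The text only says that they are not asked to stay. It neither compels withdrawal nor forbids measurement, and Withdrawal of subjects allows earlier measurements to be used. This stands too, but people who are not asked will often not be measured.

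**The scope may be narrower.** The exception follows a sentence on stopping study product, so it may cover only those who both stop and have an SAE. That would reduce the numbers. The missingness would still be tied to the event.

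**The SAP does part of the work.** It tabulates losses with reasons by group (6c), reports missing primary data by arm, compares drop-outs with those who have complete outcome data, and imputes as a sensitivity analysis (7d). These make the problem visible but do not test the missing-at-random assumption.

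**The primary model need not contain the event.** This is correct. Adjusting the primary ANCOVA for a post-randomisation event that treatment may affect could itself introduce bias. The place for SAE status is the imputation model.

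**Welfare.** Not pressing people to perform maximal-effort tests after a serious event is defensible. An invitation limited to what they are willing and judged able to do respects that.

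**Timing.** The SAP, dated May 2024, describes randomisation in the past tense. A protocol change may come too late for some or all visits, so an analysis-side remedy is also needed.

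**Conclusion.** The point holds as a missing-data weakness that is cheap to reduce. A rule stated twice ties missing 24-week leg power to a post-randomisation health event, and no named analysis repairs or probes it.

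The size cannot be derived from the documents. It is zero if loss and shortfall are equal between levels, and about 0.2 to 2.4 points in either direction under the assumed ranges. With few SAEs it would probably be small.

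Two stronger readings are not supported. One is that the treatment effect will be overstated: that needs more loss, or a larger shortfall, in the active level, and the documents give no sign of either. The other is that the rule costs power, for example 62% at a true effect of 5 points rather than 77.5% at 6 (t distribution, SD 12, 60 per level). The 62% is simply the power at a smaller true effect. If the true effect were 5 and bias moved the estimate's centre to 6, the trial would reject about 77.5% of the time. That is too many rejections, not too few.

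**What to change.** **Protocol.** Leave the clinical handling of serious events as it is. Add a sentence that separates leaving study product from leaving outcome measurement: participants with an SAE are invited to give whichever 12- and 24-week measurements they are willing and judged able to give, and are analysed as randomised. The means exist already. SAP 6c has a withdrawal level that keeps follow-up and data collection, and the protocol's Muscle Measures and Physical Activity section allows testing on another day.

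**SAP, for visits already missed.** Before the final analysis, (a) report 24-week values missing because of an SAE, by arm; (b) add SAE status to the imputation model; and (c) prespecify a delta or tipping-point analysis by arm, in which the imputed values of participants lost after an SAE are lowered by a range of shortfalls, including unequal ones. Leave the primary ANCOVA unchanged.

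**Cost.** One protocol sentence, a short SAP addition and a few more participant contacts. Some participants will be unable to do the leg press, so some values will stay missing and the sensitivity analysis is needed in any case.
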